Other mobility measures will also be examined as secondary outcomes in models otherwise identical to those in a, b, and c. The analyses will be repeated for cognition, with the speed obtained on Trailmaking B at T_{36} as the primary outcome and other cognitive measures as secondary outcomes. Additional secondary analyses will use logistic and ordinal models with the same predictors and incontinence presence and severity, respectively as outcomes; the progression model (c) will be fit as binary or ordinal generalized linear mixed models.

Hypothesis 4: Reduced total WMH and decreased markers of tissue damage on DTI at T_0 and at T_{36} are linked to better mobility at T_{36} . (Paths B+E)

The same outcomes will be used for this hypothesis as in hypothesis 1, with identical analyses except that WMH, and DTI indices (FA and MD) as continuous variables will be the primary predictor of interest. The power for this hypothesis as expressed as increased in explained variability (R^2) will be the same as for hypothesis 1: 85% power to achieve an increase in R^2 of 0.0533; we actually observed an increase in R^2 of 0.1658, to 0.2925, as the effect of tWMH, corresponding to a reduction in gait

velocity of 0.0063 m./sec. for each 0.1% increase in tWMH. The analyses will be repeated for gait velocity at T₁₈ with a model corresponding to analysis b, and for the following progression model replacing the model for analysis c:

$$Y_{i0} = b_{i0} + \beta_C (X_{i0}) + \text{cross sectional covariates} + \text{residual error}$$

$$Y_{i18} = b_{i0} + \beta_C (X_{i0}) + \beta_L (X_{i18} - X_{i0}) + \text{cross sectional covariates} + \text{longitudinal covariates} + \text{residual error}$$

$$Y_{i36} = b_{i0} + \beta_C (X_{i0}) + \beta_L (X_{i36} - X_{i0}) + \text{cross sectional covariates} + \text{longitudinal covariates} + \text{residual error}$$

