Here, Y_{i0} , Y_{i18} , and Y_{i36} are the outcomes (mobility or imaging) at T₀, T₁₈ and T₃₆ for study participant i , X_{i0} , X_{i18} , and X_{i36} the tWMH at T₀, T₁₈ and T₃₆ for study participant i , and b_{i0} is a random intercept that is used to take into account the fact that repeated measurements on individuals are not independent. The model will be fit as a linear mixed model³⁷. Again the other β_j 's are fixed effects although we will consider the possibility that treating them as random effects will add to the model fit. The parameters of interest are β_C and β_L , the cross-sectional and longitudinal effects of the imaging measures on mobility over the 36-month follow-up. As secondary analyses we will consider interactions with treatment group and nonlinear effects in time. Analyses will be repeated for the other mobility and cognitive measures, also as linear mixed models, and urinary incontinence presence/severity as binary and ordinal generalized linear mixed models.

Hypothesis 5: Total WMH at T₀ and at T₃₆ mediate the effect of treatment group, showing that

the mechanism by which reduced ABP is linked to better mobility occurs by reducing total WMH.(Paths C - A&B) Mediation models allow the evaluation of hypotheses using biological mechanisms. In this case, we believe that much of the salutary effect of reduced ABP results from reduced WMH. Assessing mediation involves estimating direct effects (Path C, above) and indirect effects (Paths A and B, above) in multistage predictor models by adding potential mediators to models describing the effect of a predictor on the outcome. To the extent by which WMH mediates the effect of BP, the effect of BP will be reduced in the model that includes WMH compared to the model not including WMH. We saw this in our observational study, as the adjusted effect of SBP in the pseudo-treatment group was reduced

from a .15 m/sec. to a .1 m/sec. difference in gait velocity when WMH was added as a model predictor.

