Here, x_i is the treatment group indicator for participant i as in (1); Y_{i1} is the mobility score for participant i at time 1 (baseline); Y_{i2} is the mobility score for participant i at time 2 (36 month follow-up); β_0 is interpreted as the average mobility score at baseline in the reference group; β_C is interpreted as the difference in the average mobility score at baseline between the intervention group and the reference group and will be zero if the two groups are exactly comparable in their baseline values; β_L is interpreted as the average change in mobility between 36 month follow up and baseline in the reference group; β_T is interpreted as the difference average change in mobility between 36 month follow up and baseline between the intervention group and the reference group and thus the parameter of primary interest; γ_i is a random intercept for participant i that addresses the correlation in mobility across the two time points; and ε_{i1} and ε_{i2} are the residual error terms at baseline and follow-up, respectively.

This analysis will be repeated for each mobility parameter (gait speed, four stair ascent and descent time, supine to sit time), cognition scores (Trailmaking A and B, Stroop Color & Word score, and simple reaction time), and the Geriatric Depression Scale. The timed measures – Trailmaking A and B, and simple reaction time – will be inverse-transformed so that they have a speed interpretation; this will also reduce the influence of outliers. Similarly, all analyses will be repeated as stratified analyses (b - e below).

- b. Stratified according to < or > median age
- c. Stratified according to gender
- d. Stratified according to median years of education
- e. Stratified according to a clinical diagnosis of minor or major depression (for mobility and cognition)

3. Change in urinary severity index and depression category (based on the Geriatric Depression Scale) from baseline to 3 years. These analyses will be similar to the analyses for white matter hyperintensities in (1) and for mobility and cognition in (2), but using ordinal logistic regression.
 - a. According to treatment group (primary analysis)

$$\log(Y_{i1} > k / Y_{i1} \leq k) = \beta_{0k} + \beta_C x_i + \gamma_i$$

$$\log(Y_{i2} > k / Y_{i2} \leq k) = \beta_{0k} + \beta_C x_i + \beta_L + \beta_T x_i + \gamma_i$$

$$k = 1, \dots, m - 1$$

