Here, x_i is the treatment group indicator for participant i (one for intervention, zero for comparison); Y_{i1} is the SF-36 score for participant i at time 1 (baseline); Y_{i2} is the SF-36 score for participant i at time 2 (36 month follow-up); β_0 is interpreted as the average SF-36 score at baseline in the reference group; β_C is interpreted as the difference in the average SF-36 score at baseline between the intervention group and the reference group and will be zero if the two groups are exactly comparable in their baseline values; β_L is interpreted as the average change in SF-36 between 36 month follow up and baseline in the reference group; β_T is interpreted as the difference average change in SF-36 between 36 month follow up and baseline between the intervention group and the reference group and thus the parameter of primary interest; γ_i is a random intercept for participant i that addresses the correlation in SF-36 across the two time points; and ε_{i1} and ε_{i2} are the residual error terms at baseline and follow-up, respectively. Above analysis will be repeated for Sleep Scales (Pittsburgh Sleep Quality Index, and Epworth Sleep scale), and then as stratified analyses (b - e below) for both Sleep and SF-36 scales.

- b. Stratified according to < or > median age
- c. Stratified according to gender
- d. Stratified according to years of education
- e. Stratified according to a clinical diagnosis of minor or major depression
- f. Change from baseline in cognitive variables
- g. Changes from baseline in mobility parameters
- h. Changes from baseline in urinary function
- i. Change from baseline in WMH (%)

6. Regression of changes from baseline in WMH as a mediator of changes from baseline in mobility, cognition, urinary function and depressive symptoms. These analyses will be based on the analyses in (2) and (3), but with the addition of mediation by and interaction with WMH using the methods of Vanderweele (REF below).

$$Y_{i1} = \beta_0 + \beta_C x_i + \gamma_i + \varepsilon_{i1}$$

$$Y_{i2} = \beta_0 + \beta_C x_i + \beta_L + \beta_T x_i + \gamma_i + \theta_M (m_{i2} - m_{i1}) + \theta_{INT} x_i (m_{i2} - m_{i1}) + \varepsilon_{i2}$$

$$m_{i2} - m_{i1} = \alpha_0 + \alpha_1 x_i + \delta_i$$

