For mobility, cognition, and depression, variables are defined as in (1) with the following additions: δ_i is residual error in the model for change in WMH, and m_{i1} and m_{i2} are the values of WMH at baseline and follow-up, respectively. Some mediation measures of interest are as follows:

$$CDE = \beta_T$$

$$INT_{REF} = \theta_{INT} \alpha_0$$

$$INT_{MED} = \theta_{INT} \alpha_1$$

$$PIE = \theta_M \alpha_1$$

The controlled direct effect $CDE = \beta_T$ is the effect of treatment assignment in the absence of any WMH, $INT_{REF} = \theta_{INT} \alpha_0$ is the reference interaction between treatment assignment and WMH, $INT_{MED} = \theta_{INT} \alpha_1$ is the mediated interaction, and $PIE = \theta_M \alpha_1 x_i$ is the pure indirect effect. Combinations of these derived measures will be used to assess the degree of mediation, as described in VanderWeele. T.J. (2015). Explanation in Causal Inference: Methods for Mediation and Interaction, Oxford University Press. In particular, the proportion mediated is $\frac{INT_{REF} + INT_{MED} + PIE}{CDE + INT_{REF} + INT_{MED} + PIE}$.

Bootstrap standard errors and confidence intervals will be used for statistical inference, including estimation of standard errors and confidence intervals.

In secondary analyses, age, sex, and resultant ambulatory systolic BP at 36 months regardless of treatment assignment will be considered as mediators through similar methods. Specifically, age, sex, and systolic BP will replace $m_{i2} - m_{i1}$ in the model above and similar measures of interaction and mediation will be estimated.

7. Special Interest adverse events (falls, nervous system and vascular disorders) as related to numerous predictors of interest.

These outcomes are all count variables, so we use Poisson regression with each of the following predictors.

$$\log(\mu_i) = \log(n_i) + \beta_0 + \beta_1 x_i$$

Here μ_i is the count, n_i is the number of months in study, β_0 is the intercept with $\exp(\beta_0)$ interpreted as the rate of AE with mobility scale is zero, x_i is the predictor of interest, mobility scale and β_1 is the log rate ratio between groups and $\exp(\beta_1)$ is interpreted as the estimated ratio of rates for two subjects differing by one in their predictors of interest scale. This analysis will be repeated for the following predictors described below:

- a. Mobility variables
- b. Cognitive variables
- c. Treatment assignment
- d. Blood pressure
- e. Age
- f. Gender

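### SAP item 6 leaves WMH out of the baseline equation, so a stable link between level of function and later WMH growth can partly be reported as mediation of functional change

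*SAP*

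**What the plan says.** SAP item 6 is headed "Regression of changes from baseline in WMH as a mediator of changes from baseline in mobility, cognition, urinary function and depressive symptoms". It displays two outcome rows per patient:

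- Baseline row: β_0 + β_C x + γ_i + error.
- Month-36 row: the same, plus β_L + β_T x + θ_M (m2 − m1) + θ_INT x (m2 − m1).

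The m terms "are the values of WMH at baseline and follow-up, respectively". Only their difference is used, and only in the second row. As defined in SAP item 2, γ_i "is a random intercept for participant i that addresses the correlation in mobility across the two time points"; nothing ties it to WMH. CDE = β_T, INT_REF, INT_MED = θ_INT α_1, PIE = θ_M α_1 and the proportion mediated are all computed from this fit. For these, "Bootstrap standard errors and confidence intervals will be used for statistical inference".

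Protocol section 8.2, Hypothesis 4, is built differently. Baseline WMH stands in all three visit equations and WMH change is added at follow-up, so the model separates "the cross-sectional and longitudinal effects of the imaging measures on mobility over the 36-month follow-up". The same section calls the Hypothesis 5 mediation results preliminary because the trial is too small for formal mediation tests. Section 1.2 lists mediation by WMH as a secondary objective for mobility, cognition and urinary function.

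**The concern.** The stated question concerns change in function. For treatment the SAP handles this properly: arm has a term in both rows, so β_T is a difference in change, even though arm is randomised. WMH growth is not randomised, yet it has no counterpart in the baseline row. The fit therefore takes baseline function as unrelated to later WMH growth within arm, and no sentence states, justifies or checks this.

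Suppose slower walkers go on to accrue more WMH but do not decline any faster. WMH growth then has no relation to functional change, yet θ_M is not zero. The trial could report that WMH accrual carries part of a mobility benefit when it carries none. Bootstrapping the same model reproduces the bias.

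**Working it through.** **Inputs from the documents.** 200 randomised, 140 completers, 70 per arm (Protocol 8.3). Detectable R² gains are 0.0533 (0.1267 to 0.1800) for gait and 0.0540 (0.1162 to 0.1702) for WMH, at 85% power.

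**Assumed, because the documents do not give them.** Two-sided α of 0.05; ρ from 0.5 to 0.85; within-arm correlation κ between level of function and later WMH growth from 0 to −0.4.

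**The plan's own figure.** Item 6 states no power. For the gait analysis, f² = 0.0533/(1 − 0.18) = 0.065, λ = 140 × 0.065 = 9.1, df (1, 135), power 84.97%. For WMH, 0.0540/(1 − 0.1702) gives 85.01%. Both reproduce.

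**What θ_M estimates.** In a random-intercept model, month-36 function given baseline function has slope ρ on the baseline residual. So θ_M is the slope of Y2 − ρY1 on WMH change. If function has slope κ on WMH change at both visits, the slope for Y2 − Y1 is zero, but

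θ_M → κ − ρκ = (1 − ρ)κ.

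**Size, by hand.** Put both variables in SD units. With θ_INT in the model, θ_M is the slope in the standard arm alone, so n = 70. At ρ = 0.7 the standard error is √(1 − 0.49)/√70 = 0.714/8.367 = 0.085. At κ = −0.2 the bias is 0.3 × 0.2 = 0.06, which is 0.70 standard errors. The rejection rate is P(Z > 1.26) + P(Z < −2.66), about 11%.

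**Rejection of a true null for θ_M, nominal 5%.** Each cell gives hand calculation / simulation (n = 140, θ_INT included, up to 4,000 trials per cell):

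| κ | ρ = 0.5 | ρ = 0.7 | ρ = 0.85 |
|---|---|---|---|
| 0 | 5 / 5 | 5 / 5 | 5 / 5 |
| −0.1 | 8 / – | 6 / 5–6 | 6 / – |
| −0.2 | 16 / 16 | 11 / 10–11 | 8 / 8 |
| −0.3 | 31 / 34 | 18 / 17–20 | 11 / 11 |
| −0.4 | 49 / 57 | 29 / 29–31 | 16 / 17 |

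With WMH change and its product with arm in both rows, the simulated rate is about 4–6% throughout.

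**The reported quantity.** An R² gain of 0.0540 corresponds to an arm effect on WMH of about 0.5 SD: 0.0540/(1 − 0.1162) = 0.0611, r = 0.247, d = 2r/√(1 − r²) = 0.51. With that effect and ρ = 0.7, the bootstrap 95% interval for PIE excluded zero in 14.5% of trials at κ = −0.3 and 26% at −0.4, against 4–7% with the terms in both rows (400 trials each). In a large sample with a total effect on change of about 0.2 SD, none of it through WMH, and κ = −0.3, θ_M was −0.095. PIE was then 0.095 × 0.5 = 0.047, which is 24% of the total effect.

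**The baseline-WMH route.** When baseline WMH drives both function level and WMH growth, the SAP model rejected in about 14% of trials (ρ = 0.7). With baseline WMH in both rows the rate returned to about 5%.

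**The case against.** The strongest reply is that a change-score model is not simply the correct one. Choosing between the slope of Y2 − ρY1 and the slope of Y2 − Y1 is the familiar choice between baseline adjustment and change scores. If month-36 function depends on WMH growth only through baseline function, then baseline function confounds the WMH–outcome relation and the SAP model behaves well. In simulation at ρ = 0.7 it rejected about 5% there, while the change-score version rejected 11% (κ = −0.2) and 16% (κ = −0.3), with bias of opposite sign. This stands. The documents do not say which process holds, so a reader who infers that the change-score model should replace item 6 goes too far.

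Second, the size of κ is unknown. A reader might take −0.2 from Protocol 8.2, where R² for gait rises by 0.1658 "as the effect of tWMH, corresponding to a reduction in gait" velocity. That is a partial correlation of √(0.1658/(1 − 0.1267)) = 0.44, and halving it gives about 0.2. But 0.44 concerns WMH level, not growth; the factor of one half is an assumption; and the figure is not within arm. If the R² gains in 8.2 and 8.3 come from one sample, removing the pseudo-treatment component leaves about 0.37. Growth–level correlations of 0.3 to 0.5 (assumed) then give 0.11 to 0.18. A link is plausible, but it is not measured.

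Third, the protocol calls its mediation results preliminary, and Hypothesis 4 remains in place. The label concerns sample size, not bias. Hypothesis 4 estimates the WMH–function relation and does not supply the item 6 mediation measures.

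**Conclusion.** The point holds as a gap in specification. Item 6 rests on an unstated assumption that the protocol's own Hypothesis 4 model does not need. If a stable link between function level and WMH growth exists, about 1 − ρ of it enters θ_M and everything derived from it. The inflation is modest at plausible values: roughly 6% to 20% instead of 5% for κ from −0.1 to −0.3 at ρ = 0.7, smaller at higher ρ, and absent at κ = 0. A false PIE also needs treatment to affect WMH, which the trial expects.

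Three stronger readings are not supported:

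- **Rejection rates of a third to a half at ρ = 0.7.** Values of 32–36% at κ = −0.3 and 53–56% at −0.4 arise only if θ_INT is dropped, and the SAP includes it.
- **A link present at baseline only.** If the link had vanished by month 36, function would truly have changed with WMH growth. The SAP model would then understate that relation (about −ρκ instead of −κ), not invent it.
- **Damage to the main result.** The primary gait analysis does not use this model.

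The calculations cover the linear outcomes; the ordinal urinary version was not simulated.

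**What to change.** In SAP item 6, add baseline WMH (m_i1) to both the baseline and the month-36 equations, following Protocol Hypothesis 4, and compute CDE, INT_REF, INT_MED and PIE from that fit. This closes the route through baseline WMH and keeps the baseline rows of patients who drop out. It does not remove a link that arises in another way.

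For that reason, report a companion analysis with WMH change and its product with arm in both rows. For complete pairs this is the regression of Y2 − Y1 on arm, WMH change and their product. State that the two versions make different assumptions about baseline function, and that mediation will be interpreted cautiously if they disagree. If the same change is made to the ordinal urinary model, check its behaviour first.

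The cost is one or two model terms and some SAP wording, with no new data. In the companion version the standard error of θ_M rises by a factor of about √(2/(1 + ρ)): 1.12 at ρ = 0.6, 1.08 at 0.7 and 1.05 at 0.8. That version also uses only patients with a month-36 MRI, about 140 of 200 on the plan's projection.

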8.2 Hypotheses and Statistical Analyses

The Figure shows graphically how our hypotheses relate to one another. Hypothesis 1 tests the combined effects of paths A, B, C, D & E i.e., the total effect of BP on mobility. Hypothesis 2 tests path A, Hypothesis 3 tests path D, Hypothesis 4 tests path B+E; together Hypotheses 2, 3 and 4 together test the effect of BP on mobility mediated through BP's effects on WMH and WM microstructure. Hypothesis 5 tests the relative importance of paths A and B to that of path C, i.e., the degree to which the effect of BP on mobility is explained by WMH. Hypothesis 6 tests the relative importance of paths D and E to that of path C, i.e., the degree to which the effect of BP on mobility is explained by changes in WM microstructure.

Hypothesis path diagram

Hypothesis 1: Intensively treating 24-h systolic BP to a goal of <130 mmHg versus standard BP control of <145 mmHg will lead to faster walking speeds at T₃₆. (Paths A&B+C+D&E)

Hypothesis 2: Intensively treating 24-h systolic BP to a goal of <130 mmHg versus standard BP

control <145 mmHg will lead to smaller total WMH volume. (Path A)

Hypothesis 3: Intensively treating 24-h systolic BP to a goal of <130 mmHg versus standard BP

control <145 mmHg will stabilize brain WM microstructural integrity (FA and MD) at T₃₆. (Path

D) We will perform 3 sets of analyses for hypotheses 1, 2 & 3:

- a. Multiple linear regression will be performed with treatment group (intensive vs. standard) as the predictor of interest. Gait velocity at T₃₆ is the primary outcome for hypothesis 1, WMH at T₃₆ is the primary outcome for hypothesis 2, and DTI indices (FA and MD) are the primary outcomes for hypothesis 3. The analysis will be intention-to-treat. Age, sex, and 24 hour SBP at T₀ (baseline) will be included as covariates, along with other demographic factors for which the treatment groups are not comparable. **The analysis for hypothesis 1 is the proposal's primary efficacy analysis and thus the proposal is powered to address this analysis (see Sample size estimation).**

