**Intensive Versus Standard Blood Pressure Lowering to Prevent
Functional Decline in Older People**

NCT01650402

Statistical Analysis Plan

IRB Approval Version 9/25/2018

INFINITY Statistical Analysis Plan (modification)

IRB Review
IRB NUMBER: IE-11-155S-2
IRB APPROVAL DATE: 09/25/2018

Principal Investigators: [name], [name]
Senior Statistician: [name]
Project Statistician: [name], MS
Date: 24 September 2018

Amendment 1.1

The primary objective of the INFINITY Trial is to assess causality between 24-hour systolic BP levels and preservation of mobility, cognitive and urinary function associated with reduced accrual of small vessel disease of the subcortical white matter in people over the age of 75 years.

A key hypothesis of the trial is that intensive treatment of 24-hour systolic BP to levels of 130 mmHg or less will result in improved gait time, stair descent time, and maximal gait velocity compared to treatment of 24 hour systolic BP to levels of 145 mmHg or less. This separation of ambulatory BP goals should achieve at least a ≥ 10 mmHg differences between groups over time. Previously, this difference has been shown to be responsible for the mobility decrements associated with WMH in older patients with systolic hypertension in a prospective cohort study (Circulation. 2011;124 (21):2312-9. doi: 10.1161/CIRCULATIONAHA.111.037036).

Prior to database lock of this trial in October 2018, we have added several secondary analyses to be pre-specified with their rationale as needed.

1. Change in white matter hyperintensity (%) (WMH) from baseline to 3 years
 - a. According to treatment group (primary analysis)

$$\begin{aligned} Y_{i1} &= \beta_0 + \beta_C x_i + \gamma_i + \varepsilon_{i1} \\ Y_{i2} &= \beta_0 + \beta_C x_i + \beta_L + \beta_T x_i + \gamma_i + \varepsilon_{i2} \end{aligned} \tag{1.1}$$

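### SAP item 6 estimates mediation by WMH change without baseline covariates, so if treatment alters WMH, shared causes of WMH growth and functional decline can be counted as mediation.

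*SAP*

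**What the plan says.** SAP item 6 introduces its models with "These analyses will be based on the analyses in (2) and (3), but with the addition of mediation by and interaction with WMH". It has two parts. The mediator equation is "m_{i2} - m_{i1} = \alpha_0 + \alpha_1 x_i + \delta_i", which is WMH change on arm alone. The outcome equation takes the item 2 model (arm, visit, arm by visit, random intercept) and adds to the follow-up line "\theta_M (m_{i2} - m_{i1}) + \theta_{INT} x_i (m_{i2} - m_{i1}) + \varepsilon_{i2". Age, sex and baseline blood pressure appear in neither. Baseline WMH appears only inside the difference.

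The indirect effect is "PIE = \theta_M \alpha_1". The controlled direct effect (CDE) is β_T, which the SAP says "is the effect of treatment assignment in the absence of any WMH". Inference is by bootstrap. In secondary analyses, "age, sex, and resultant ambulatory systolic BP at 36 months regardless of treatment assignment will be considered as mediators".

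The protocol is specified differently (section 8.2, Hypotheses and Statistical Analyses). For hypotheses 1 to 3, age, sex and 24-h systolic pressure at "baseline) will be included as covariates, along with other demographic factors for which the treatment groups are not comparable". The progression model for hypothesis 4 has separate terms for baseline WMH and WMH change, plus covariates. Hypothesis 5 multiplies path coefficients and treats the result as preliminary because the trial is too small for formal mediation tests. The SAP says of its contents that "we have added several secondary analyses to be pre-specified with their rationale as needed". It does not say whether item 6 replaces hypothesis 5.

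**The concern.** Randomisation protects α_1, the effect of arm on WMH change. It does not protect θ_M, the association of WMH change with the outcome. θ_M is a causal effect only if the common causes of WMH growth and functional decline are in the model. The random intercept at best removes stable differences in level, whereas these causes act on change. A bootstrap interval describes sampling error around the biased value.

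The documents point to such causes: in the sample-size section, age, sex and baseline pressure explain part of both gait velocity and WMH. Item 6 does name age and sex, but as mediators. Treatment cannot change either, so neither can lie on the path from treatment to outcome.

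Three secondary objectives (protocol section 1.2) concern mediation by WMH, and section 3 presents WMH accrual as the mechanism of decline. The mediated share is therefore the number a reader would take as evidence of mechanism.

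The CDE description is a separate misstatement. The mediator is WMH change, so the CDE refers to zero change, in participants who must all have at least 0.5% WMH to enter (protocol section 4.1).

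**Working it through.** **1. The plan's own figures.** The SAP gives none for mediation. From protocol section 8.3 (Sample Size and Randomization): N = 140, R² increase 0.0533 to 0.1800. f² = 0.0533/(1 − 0.1800) = 0.065; λ = 140 × 0.065 = 9.1. A noncentral F test with 1 and 135 df and α = 0.05 (assumed; none is stated) gives power 84.97%, against the stated 85%. For WMH (0.0540 to 0.1702) it is 85.01%. Both reproduce.

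The cohort's mediation figures are also coherent. Adding WMH reduced the gait difference from 0.15 to 0.10 m/s, which is 33%. The product method uses a WMH difference of 0.93% and a slope of 0.0063 m/s per 0.1%, or 0.063 per 1%: 0.93 × 0.063 = 0.0586 m/s, which is 39% of 0.15.

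**2. How the bias travels.** With no arm-by-WMH interaction, total effect = β_T + θ_M α_1. Arm is randomised, so α_1 and the total are unbiased, and bias(PIE) = α_1 × bias(θ_M). What PIE gains, the CDE loses. If α_1 = 0, expected PIE is 0. Shares below are PIE/total, which equals the SAP's proportion mediated when θ_INT = 0.

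**3. Size from the protocol's R² values.** Inputs (section 8.3): R² on age, sex and baseline pressure of 0.1267 (gait) and 0.1162 (WMH); R² increases for group of 0.1082 and 0.0861. Assuming equal groups and a group term uncorrelated with the covariates:

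- SD of gait = 0.15 × 0.5/√0.1082 = 0.228 m/s
- SD of WMH = 0.93 × 0.5/√0.0861 = 1.585%

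Unadjusted θ_M = θ_M(1 − R²m) + ρ√(R²y R²m) × SDy/SDm, where ρ is the alignment of the two covariate effects.

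True θ_M = 0, ρ = 1: √(0.1267 × 0.1162) × 0.228/1.585 = 0.1213 × 0.1439 = 0.0175. PIE = 0.93 × 0.0175 = 0.0162 m/s, which is 11% of 0.15. At ρ = 0.5 it is 0.0081 m/s, 5%. Dividing by the within-arm WMH variance, as the fitted model does, gives 0.0162/(1 − 0.0861) = 0.0178 m/s, 12%.

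Adjusted θ_M = 0.063, ρ = 1: 0.063 × 0.8838 + 0.0175 = 0.073; PIE 0.068 m/s; share 45% instead of 39%. At ρ = 0.5 it is 40% instead of 39%.

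**4. Adding baseline WMH (all inputs assumed).** Let treatment lower WMH change by 0.5 and raise function by 0.4, with no WMH effect on function. Age and baseline WMH, standardised with correlation c, have coefficients a and w on WMH change and −a and −w on function. Error variance is s². With V = a² + w² + 2awc, the false share is (0.5/0.4) × V/(V + s²):

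| a, w | s² = 1, c = 0 | s² = 0.81, c = 0.3 |
|---|---|---|
| 0.2, 0 | 5% | 6% |
| 0.3, 0 | 10% | 12.5% |
| 0.2, 0.2 | 9% | 14% |
| 0.3, 0.3 | 19% | 28% |

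With both confounders in both equations it is 0.

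**5. The SAP's random-intercept model, simulated** (N = 20,000; treatment lowers WMH change by 0.4 SD; direct effect 0.05 m/s). The confounder correlates 0.34 (moderate) or 0.5 (strong) with WMH change and lowers follow-up gait by a further 0.02 or 0.04 m/s per SD. With true θ_M = 0, the reported proportion mediated was 10% and 22%, and about 0 once the confounder and its visit interaction were included. With a true share of 19% it was 27% and 37%. With α_1 = 0, PIE was within 0.0002 m/s of zero throughout.

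**The case against.** Four points deserve weight.

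- **Balance by arm.** A reader might infer that ageing and baseline lesion load will necessarily be reported as mediation. The documents do not support that. Both are balanced between arms in expectation and reach PIE only multiplied by α_1. This stands as a condition. However, a non-zero α_1 is the trial's hypothesis 2, and it is the case in which mediation would be interpreted.
- **Size.** The documents give no figure for baseline WMH as a driver of WMH growth or decline, so the upper part of the 5 to 28% range is assumption. The protocol's R² values come from an observational cohort and are not stated to be for changes. Unless the covariate effects are closely aligned, the distortion on those values is small. This stands.
- **Sampling error.** At N = 140 with moderate confounding, the simulated false PIE of 0.0048 m/s compares with a standard deviation of 0.0072. The SAP's proportion mediated ranged below 0 and above 1 in every scenario. Imprecision is the larger problem, and the protocol's preliminary label admits it. But item 6 does not repeat that label, and imprecision is no reason to keep a bias that can be removed.
- **The protocol already adjusts.** Hypothesis 5 builds on covariate-adjusted models, and the SAP calls its analyses additions without withdrawing it. So one cannot conclude that the trial has no adjusted mediation analysis. The defect is in item 6 and in its unstated relation to hypothesis 5.

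**Conclusion.** The concern holds in a conditional form. Item 6 omits baseline covariates that the protocol's own models carry, and this biases θ_M and hence PIE, INT_MED and CDE. The total effect is unaffected. The false indirect effect arises only if treatment alters WMH.

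If WMH change has no effect on function, the false share is at most about 11% of a 0.15 m/s effect on the protocol's R² values for age, sex and baseline pressure (12% with within-arm variance). It is about 5 to 28% under assumed confounding by age and baseline WMH, depending on error variance and confounder correlation. These figures are guides, since no document gives the correlations between changes.

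Two faults need no assumption: age and sex cannot be mediators of a randomised treatment, and the CDE is not the effect without WMH. As a secondary analysis that the protocol calls preliminary, this should be corrected but does not touch the primary efficacy result.

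**What to change.** In SAP item 6:

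- Add age, sex, baseline 24-h systolic pressure and baseline WMH % to the mediator equation, and to the follow-up outcome equation as visit interactions, because they act on change.
- Use age and sex as covariates or effect modifiers, not as mediators.
- State that the mediation estimates assume no unmeasured common cause of WMH change and outcome, and carry over the protocol's preliminary label.
- Say whether item 6 replaces or supplements protocol hypothesis 5.
- Describe the CDE as the treatment effect at zero WMH change from baseline, or evaluate it at the mean WMH change.

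A sensitivity analysis to residual confounding is desirable but optional, as is diabetes as a further covariate. The cost is SAP wording and a few degrees of freedom at about 140 completers. The covariates come from assessments already scheduled at or before baseline (protocol section 5.5).
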